5.4.2. ANALYSIS OF THE PRIMARY SAFETY ENDPOINT

The primary endpoint is the incidence of serious adverse events defined as occurrence of bleeding grade ≥ 3 (see Adverse Events for bleeding grading system), pneumothorax requiring chest tube placement (Grade ≥ 2 , see Adverse Events for pneumothorax grading system), post-procedure respiratory failure defined as the need for non-invasive or mechanical ventilation requiring ICU admission, or death, which have occurred within 30 days after procedure, respectively. The incidence will be calculated as the proportion of patients in whom a serious adverse event occurred divided by those who underwent the index procedure (insertion of the cryoprobe into the working channel of the bronchoscope).

As the true safety profile of the 1.1mm flexible cryoprobe with oversheath is not currently known, and no standard minimally significant difference in a combined bleeding and pneumothorax outcome (such as in this study) is known, we will use currently available literature on a comparable biopsy method, (forceps biopsy and the larger 1.9mm and 2.4mm cryoprobes).

Based on review of the published literature (**Table 1**), we conservatively estimate the current combined bleeding and pneumothorax proportion to be 30% for transbronchial biopsy in standard practice. The procedure will be considered safe if the final proportion of serious adverse events is 30% or less. This will infer a standard of safety for the 1.1mm flexible single-use cryoprobe with oversheath comparable to current transbronchial biopsy standard of care.

Table 1: Literature review of bleeding and pneumothorax rates

Author	Definition of bleeding as per study	Number of patients in CBx, n (%)	Number of patients in FBx, n (%)
Aktas et al. (2010) ¹³ , (n = 41); All performed CB and FB; CB = 41, FB = 41	No bleeding Simultaneous bleeding Mild: cold water + adrenaline Moderate: APC application Severe : hemodynamic compromise Pneumothorax	26 (63.4) 5 (12.2) 8 (19.5) 2 (4.9) 0 (0) not reported	27 (65.9) 5 (12.2) 9 (21.9) 0 (0) 0 (0) not reported
Hetzell et al. (2012) ¹⁴ , (n = 593); CB = 296, FB = 297	No bleeding Mild: suctioning Severe: ice cold saline, diluted vasoconstrictive drug, balloon tamponade, APC, MV, conversion to rigid bronchoscope. Pneumothorax	59 (19.9) 183 (61.8) 54 (18.2) not reported	91 (30.6) 153 (51.5) 53 (17.8) not reported
Pajares et al. (2014) ³ , (n = 77) ; CB = 39, FB = 38	Grade 0: no bleeding Grade 1: suction Grade 2: occlusion, use of endoscopic procedures and/or ice cold saline Grade 3: hemodynamic compromise, admission to ICU Pneumothorax	5 (12.8) 12 (30.8) 22 (56.4) 0 (0) 3 (7.7)	8 (21.1) 17 (44.7) 13 (34.2) 0 (0) 2 (5.2)
Fruchter et al. (2014) ¹⁵ , (n=75) CB single arm	No bleeding Significant bleeding Pneumothorax	70 (93) 3 (4) 2 (2.6)	NA
Hagmeyer et al. (2016) ¹⁶ , (n=32) CBx only	No or mild bleeding Moderate: wedge of bronchoscope severe: use of bronchial blocker or blood transfusion Pneumothorax	8 (25) 17 (53) 6 (19)	NA NA NA

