Population:	
Inclusion Criteria:
 
 • Male or Female, \geq 18-years-old • Scheduled to undergo bronchoscopy with transbronchial biopsy as the standard medical care determined by their treating pulmonologist 
Exclusion Criteria:
 
 • Pregnant or nursing females, or females of child bearing potential who refuse to take a pregnancy test prior to enrollment • Individuals with current or recent systematic conditions, such as uncontrolled hypertension (systolic $>$ 200 mmHg or diastolic $>$ 110 mmHg), type 1 diabetes, severe pulmonary hypertension, acute kidney injury, stroke (within the last 6 months) or myocardial infarction (within the last 3 months) • Presence of bleeding disorder • Platelet count $<$ 50,000 • Current use of systemic anticoagulation or antiplatelet therapy without the ability to hold therapy for the recommended amount of time prior to an invasive procedure (aspirin monotherapy is acceptable)

	
 • International Normalized Ratio (INR) <1.5 • Robotic Bronchoscopy • Do Not Resuscitate (DNR) status • Do Not Intubate (DNI) status
Endpoints:	
The primary endpoint will be the number of serious adverse events in those enrolled in the study. Serious adverse events are defined as:
 
 • Grade 3 or 4 bleeding • Pneumothorax requiring chest tube placement (Grade ≥ 2) • 30-day respiratory failure and death. 
Secondary endpoints include minor adverse events (bleeding Grade 1 or 2), pneumothorax not requiring chest tube placement (Grade 1), histologic accessibility, diagnostic yield

Statistical Methodology	This study is designed to ensure the serious adverse event rate using the 1.1mm flexible single-use cryoprobe with oversheath will not exceed the expected serious adverse event rate of transbronchial biopsy using standard biopsy procedures (30%)
Safety Monitoring	After each 10 consecutive patients are enrolled, the DSMB will review safety. Additionally, after each serious adverse event, the study will be halted until adjudicated by the DSMB.

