5.2. STATISTICAL HYPOTHESES

1. To determine the serious adverse event rate of a 1.1mm flexible single-use cryoprobe with oversheath for transbronchial bronchoscopic biopsy.

We hypothesize that the serious adverse event proportion using the novel smaller, 1.1mm flexible single-use cryoprobe with oversheath will not exceed 30%, the adverse event proportion for the current standard method of transbronchial biopsy using forceps.

2. To determine baseline performance characteristics for the use of the 1.1mm flexible single-use cryoprobe with oversheath.

We hypothesize that data generated during the performance of this safety trial will generate meaningful descriptive statistics for pathologic evaluation (histologic adequacy), procedural characteristics (activation time, number of biopsies taken, type of airway used), and diagnostic yield across various disease states necessitating transbronchial biopsy. This descriptive data will be crucial in the planning of future clinical trials.

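### Section 5.4.2 infers standard-of-care safety from an SAE proportion of 30% or less, but the plan does not establish 30% as the serious-event rate of standard transbronchial biopsy

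*Combined protocol and SAP*

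**What the plan says.** The primary endpoint (sections 2.2 and 5.4.2) is the proportion of patients with at least one of four events: bleeding of grade 3 or higher, pneumothorax needing a chest tube, respiratory failure with ventilatory support and ICU admission, or death, within 30 days. The denominator is patients in whom the cryoprobe entered the working channel.

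Section 5.4.2 then gives a decision rule, "The procedure will be considered safe if the final proportion of serious adverse events is 30% or less", and draws an inference from it: "This will infer a standard of safety for the 1.1mm flexible single-use cryoprobe with oversheath comparable to current transbronchial biopsy standard of care".

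The 30% is described in three ways:

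- Synopsis, Statistical Methodology: the SAE rate with the device "will not exceed the expected serious adverse event rate of transbronchial biopsy using standard biopsy procedures (30" (quotation cut before the percent sign).
- Section 5.2: it "will not exceed 30%, the adverse event proportion for the current standard method of transbronchial biopsy using forceps".
- Section 5.4.2: "we conservatively estimate the current combined bleeding and pneumothorax proportion to be 30% for transbronchial biopsy in standard practice".

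The stated comparator also shifts. Section 5.2 refers to forceps alone, whereas section 5.4.2 names "forceps biopsy and the larger 1.9mm and 2.4mm cryoprobes" as the literature used. Section 3.9 uses 30% again in the batch halting rule. Sections 5.1 and 5.7 say that the study is not powered for a statistical conclusion and that no reliable data exist to power it.

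**The concern.** A ceiling on serious events supports a statement about comparability only if it is itself a serious-event rate, for the same kind of biopsy, under matching definitions. Section 5.4.2 puts a figure of unstated severity on one side and a strict four-part SAE composite on the other. If the 30% includes milder events, a device could cause clearly more serious harm than standard biopsy and still be reported as comparable.

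This is the only stated verdict on the primary endpoint, so it is likely to be carried into the report. What is at stake is what the trial may conclude. Data collection and the protection of participants are not affected.

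**Working it through.** **Inputs.** Forceps columns of Table 1. The biopsy type comes from the titles in section 13.

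| Study | Forceps n | No bleeding | More than suction needed | Pneumothorax |
|---|---|---|---|---|
| 41-patient lung cancer study, titled endobronchial | 41 | 27 | 9 | not reported |
| 593-patient multicentre trial, titled endobronchial | 297 | 91 | 53 | not reported |
| 77-patient randomised trial in interstitial lung disease | 38 | 8 | 13 | 2 |
| Total | 376 | 126 | 75 | 2/38 |

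In the 41-patient study, the 5 bleeds labelled simultaneous carry no stated treatment and are taken as needing no more than suction.

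**Step 1: try to reproduce the 30%.** The plan gives no formula, so several cut-offs were tried.

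- Any bleeding, pooled: (376 − 126)/376 = 250/376 = 66.5%. By itself, the 41-patient row gives 14/41 = 34.1%.
- More than suction, pooled: 75/376 = 19.9%. Adding pneumothorax, 2/38 = 5.3%, gives 25.2%.
- More than suction, unweighted mean of the three studies: (22.0% + 17.8% + 34.2%)/3 = 24.7%. Adding 5.3% gives 29.9%.

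Only the last comes close. It is a post hoc reconstruction, not a derivation found in the plan. It counts cold water with adrenaline, iced saline and any pneumothorax. Section 3.7.5 places iced saline in bleeding Grade 2, which section 2.3 makes a secondary endpoint. Bleeding becomes serious only at Grade 3, when a bronchial blocker is inflated.

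**Step 2: can Table 1 give a serious-event rate?**

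- It has no chest-tube, respiratory-failure or death counts. Ventilation and ICU admission appear only inside bleeding categories.
- Two of the three forceps rows do not report pneumothorax.
- The 593-patient trial has one category, "Severe: ice cold saline, diluted vasoconstrictive drug, balloon tamponade, APC, MV, conversion to rigid bronchoscope". The 77-patient trial similarly puts occlusion and cold saline in one grade. Together these rows hold 297 + 38 = 335 of 376 forceps patients (89.1%), and the serious share cannot be separated. Their cryoprobe columns use the same categories.
- 41 + 297 = 338 of 376 forceps patients (89.9%) come from studies titled endobronchial, whereas the claim concerns transbronchial biopsy.

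**Step 3: what the less affected rows allow.**

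- Forceps row not titled endobronchial (n = 38), bleeding and pneumothorax only: from 0/38 = 0%, if no grade 2 bleed and no pneumothorax was serious, to (13 + 2)/38 = 39.5%, if all were and none overlapped. The upper end is an extreme corner, and both limits ignore sampling error.
- 75-patient cryoprobe row, titled transbronchial: 3 significant bleeds (4%) and 2 pneumothoraces (2.6%). Significant is not defined, and there is no forceps arm.
- The 32-patient cryoprobe row shows three values for four labels in the text available, so nothing here rests on it.

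**Step 4: what the rule does.** With 50 analysed, 30% or less means at most 15 patients with an SAE. The probability of passing is the sum over k = 0 to 15 of C(50,k) p^k (1−p)^(50−k), where p is the true SAE rate.

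| True SAE rate | 20% | 25% | 30% | 35% | 40% |
|---|---|---|---|---|---|
| Probability of passing | 96.9% | 83.7% | 56.9% | 28.0% | 9.6% |

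At 15/50 the exact (Clopper-Pearson) 95% CI is 17.9% to 44.6%. These figures do not depend on the standard-care rate, which the plan leaves open. If that rate were 10% (an assumption), a device with twice the rate would pass with probability 96.9%. If it were 5% (an assumption), one with four times the rate would pass equally often.

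**The case against.** The best defence has four parts.

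**The labels may be one label.** The sentence in section 5.2 begins with the serious adverse event proportion, so its later phrase may simply be short for it. Section 5.4.2 says that "no standard minimally significant difference in a combined bleeding and pneumothorax outcome (such as in this study) is known", which ties the composite to this trial's endpoint. This is fair, and the wording by itself is the weaker half of the point. Even if a serious-event rate was meant throughout, Table 1 does not supply one.

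**The study disclaims power.** Sections 5.1 and 5.7 do so openly, and the lack of a test or interval would be a modest criticism by itself. But the disclaimer concerns precision. It does not withdraw the inference in 5.4.2, and a larger sample would not cure a benchmark that counts different events.

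**Participants are protected.** Under sections 3.9 and 5.6 every SAE pauses recruitment until the DSMB has adjudicated it, and the SAE proportion is reported in any case. This stands, and it confines the point to the conclusion drawn.

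**The direction of error is not shown.** This also stands. A reader might infer that Table 1 proves 30% too lenient, since the 29.9% reconstruction counts milder events and the 75-patient row lies far lower. The documents do not go that far: the reconstruction is not the plan's, the 75-patient row is cryoprobe-only with an undefined severity term, and the 38-patient forceps row does not exclude a higher rate. Nor should one infer that the errors are evenly balanced. The 39.5% needs every grade 2 bleed in that arm to be serious here, although the undefined term occlusion could mean wedging, and the arm had no haemodynamic compromise or ICU admission. A reader might also infer that 30% cannot be an all-grade rate. It does not match the pooled 66.5%, but the 34.1% in one row prevents a firm exclusion.

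**Conclusion.** The concern holds. The plan does not show that 30% is the serious-event rate of standard transbronchial biopsy, and Table 1 cannot show it. An SAE proportion at or below 30% therefore does not support the comparability statement, and one above it would not refute comparability. Calling the estimate conservative is unsupported. The nearest reconstruction points towards a lenient ceiling without proving it.

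In size, up to 15 SAE patients in 50 earn the verdict, and true SAE rates of 20% and 25% earn it in 96.9% and 83.7% of trials. These probabilities assume that all 50 participants reach the index procedure and that outcomes are independent with a common rate. The Table 1 figures assume that its categories mean what their labels say, and that a title naming endobronchial biopsy describes the biopsies done.

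**What to change.** 1. In section 5.4.2, replace both the sentence declaring the procedure safe and the sentence inferring comparability, and delete the word *conservatively*, unless a like-for-like serious-event basis for the 30% is stated. Changing only the comparability sentence would leave the safety verdict standing beside a mere reference value. Possible wording:

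   *The proportion of patients with at least one SAE will be reported with an exact 95% CI. 30% is a reference value; Table 1 does not give serious-event rates for transbronchial forceps biopsy, so an observed proportion at or below it will not by itself be taken to show that the procedure is safe or comparable to standard care.*

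2. Describe the 30% identically in the synopsis, section 5.2 and section 5.4.2, including whether the comparator is forceps alone. Do not call it an expected SAE rate without a source.

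3. Section 3.9 uses the same figure for halting. Its stated basis must be reconciled with section 5.4.2; no threshold is proposed here.

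The cost is wording in three places, a note on section 3.9, and one interval from data already collected. A further literature review is needed only if the sponsor wants to keep the comparability claim. The downside is that the trial would claim less.

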3.9. STUDY HALTING RULES

Any SAE will serve as a stopping rule. The DSMB will convene to adjudicate the event. Enrollment will resume if the SAE is adjudicated by the DSMB. Additionally, if the SAE rate rises above 30% for two consecutive batches (10 cases per batch), the study will be halted.

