5. STATISTICAL CONSIDERATIONS

5.1. STATISTICAL AND ANALYTICAL PLANS

The study is not powered to make a statistical conclusion due to the small sample size and the safety phase in which the treatment is. As the true safety profile of the 1.1mm flexible single-use cryoprobe with oversheath is not known, we will base our statistical plan based on current standard method for transbronchial biopsy, forceps biopsy.

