5.4. DESCRIPTION OF STATISTICAL METHODS

5.4.1. GENERAL APPROACH

This is a multi-centered, prospective, single arm trial aimed at establishing the safety profile of a novel 1.1mm flexible single-use cryoprobe with oversheath. Secondary outcomes will be descriptive procedural characteristics that will be used to power future trials.

All continuous data will be presented as means with standard deviations. Categorical data will be represented by percentages. Statistical comparisons will be made using linear and logistic regression

analysis where applicable. Sensitivity, specificity, positive and negative predictive value and accuracy of all procedures will be calculated.

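### Section 5.4.2 declares the procedure safe and comparable to standard care from the observed proportion alone, with no interval, margin or error rate, in a study that disclaims any statistical conclusion

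*Combined protocol and SAP*

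**What the plan says.** Section 5.4.2 sets the decision rule, "The procedure will be considered safe if the final proportion of serious adverse events is 30% or less", and then the inference drawn from it: "This will infer a standard of safety for the 1.1mm flexible single-use cryoprobe with oversheath comparable to current transbronchial biopsy standard of care". The same section concedes that "no standard minimally significant difference in a combined bleeding and pneumothorax outcome (such as in this study) is known".

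For reporting, Section 5.4.1 offers only "Categorical data will be represented by percentages". Section 5 plans no confidence interval, significance level or power for the primary endpoint.

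The documents differ on what the study can conclude:

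- Synopsis, Statistical Methodology: "This study is designed to ensure the serious adverse event rate" will not exceed the 30% expected with standard biopsy.
- Section 5.2 hypothesises that the SAE proportion "will not exceed 30%, the adverse event proportion for the current standard method of transbronchial biopsy using forceps".
- Section 5.1: "The study is not powered to make a statistical conclusion due to the small sample size".
- Section 5.7 says no reliable data exist for powering the study. It also asserts that the SAE rate estimate will have stabilised by 50 cases, without giving a precision.

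Two safety provisions bear on the result. Under Sections 3.9 and 5.6, any SAE halts recruitment until the DSMB has adjudicated it. Section 3.9 adds that "if the SAE rate rises above 30% for two consecutive batches (10 cases per batch), the study will be halted".

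**The concern.** A purely descriptive pilot of 50 patients needs no power calculation, and the disclaimers in 5.1 and 5.7 would then be enough. Section 5.4.2 does not stay descriptive. It fixes in advance the only conclusion to be drawn on the primary endpoint and rests it on a point estimate. Sampling error plays no part: 15/50 earns the same label as 2/50. The word 'comparable' has no defined meaning either, because no margin is set and the section says none is known.

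Readers of the trial report would take 'safe' and 'comparable' as findings, although the plan says elsewhere that the study cannot support a statistical conclusion.

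**Working it through.** **Inputs.** n = 50 (5.7); threshold 30% (5.4.2); batches of 10 (3.9). All 50 patients are assumed to reach the index procedure, which defines the denominator in 5.4.2. The true SAE rates below are illustrative values chosen for this check and are not in the documents.

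**The plan's own figure.** The sample size of 50 cannot be reproduced, because 5.7 gives no error rate, power, margin or precision target.

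**Cut-off.** 0.30 × 50 = 15, so the procedure is called safe when X ≤ 15.

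**Chance of the 'safe' label if no review stops the trial.** P(X ≤ 15) = Σ C(50,k) pᵏ(1−p)⁵⁰⁻ᵏ, summed over k = 0 to 15.

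| True SAE rate | P(called safe) |
|---|---|
| 25% | 83.7% |
| 30% | 56.9% |
| 35% | 28.0% |
| 40% | 9.6% |
| 45% | 2.2% |

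**Effect of the batch halt.** The text does not say whether the halt is permanent. Nor does it say whether the SAE rate is taken per batch, cumulatively or pooled over two batches. Suppose the halt is permanent and a halted study is not called safe. Then P(not halted and X ≤ 15) is found by enumerating five independent Binomial(10, p) batches. Figures in brackets apply if a trigger first reached at the last batch does not count.

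| Reading of the batch rule | True rate 35% | True rate 40% |
|---|---|---|
| At least 4/10 in each of two consecutive batches | 23.2% (24.4%) | 7.6% (8.1%) |
| Running rate above 30% at two consecutive looks | 21.5% (21.5%) | 7.0% (7.0%) |
| More than 6/20 over two adjacent batches | 8.3% (12.3%) | 2.2% (3.6%) |

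**Halt after any SAE.** At a true rate of 35%, 50 × 0.35 = 17.5 patients with an SAE are expected, so the DSMB would meet often. The protocol states no criterion for ending the trial after such a review, so the effect cannot be calculated.

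**Precision at n = 50.** The exact (Clopper-Pearson) 95% limits are the 2.5% quantile of Beta(x, n−x+1) and the 97.5% quantile of Beta(x+1, n−x).

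| Result | Estimate | Exact 95% CI | Distance from estimate (points) |
|---|---|---|---|
| 5/50 | 10% | 3.3% to 21.8% | −6.7 / +11.8 |
| 10/50 | 20% | 10.0% to 33.7% | −10.0 / +13.7 |
| 15/50 | 30% | 17.9% to 44.6% | −12.1 / +14.6 |

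Even at 10/50 the upper limit lies above the 30% reference.

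**The case against.** The strongest reply has four parts.

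- **28.0% is a ceiling.** The protocol prescribes reviews, and the wording of the batch rule most naturally means each batch taken separately. Section 3.9 gives a resumption route after a single SAE but none after the batch trigger, which suggests a permanent halt. On that reading the figure is 23.2%. The DSMB charter mentioned in 3.8 may hold further criteria. This stands, and 28.0% should be read only as an upper figure. But these provisions govern conduct; none is described as setting a rule for the final proportion, and none puts an interval on it.
- **A true rate of 35% or more may be unlikely.** In Table 1, severe bleeding was 0/41 in both arms of the first study. In the 77-patient study, grade 3 bleeding was 0/39 and 0/38, with pneumothorax in 7.7% and 5.2%. One study's 18% for severe bleeding counts iced saline, which this protocol grades as 2. This weakens the practical risk, but 5.4.2 itself says the true safety profile is unknown. If the rate is low, an interval strengthens the report: 5/50 excludes 30% comfortably.
- **The limits are disclosed.** Sections 5.1 and 5.7 are candid. The disclosure warns the reader, but 5.4.2 still draws the conclusion.
- **A margin is not always needed.** If 30% is a fixed performance threshold, an interval compared with 30% is enough. That is correct; the missing margin matters only for the claim of comparability.

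**Conclusion.** The concern holds. The plan attaches a verdict to a point estimate that Section 5.1 says cannot carry one, and it provides no measure of uncertainty beside it. At the boundary, 'safe' would be declared with data compatible with rates from 17.9% to 44.6%. The chance of the label at an illustrative true rate of 35% is at most 28.0%, and between 8.3% and 24.4% if the batch halt is permanent, depending on its reading. The halt after any SAE may lower these values further by an unknown amount. All figures assume 50 analysed patients; fewer would generally widen the intervals. The contradiction and the missing interval do not depend on the illustrative rates. This should be corrected, and the correction is one of wording and reporting.

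**What to change.** Keep n = 50 and bring the wording into line with Section 5.1.

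1. **Section 5.4.2.** Report the SAE proportion with its exact (Clopper-Pearson) 95% confidence interval. Replace the two verdict sentences with a descriptive statement of the estimate and interval beside the 30% reference. State that the hypothesis in 5.2 is not formally tested. Add that the comparison is not like for like: 5.2 sets a serious adverse event proportion against an adverse event proportion, and 5.4.2 takes 30% from a combined bleeding and pneumothorax proportion.
2. **Synopsis.** Say that the study is designed to estimate the SAE rate, not to ensure that it stays below a limit.
3. **Section 5.7.** Replace the claim of stability with the intervals that n = 50 gives at 5/50, 10/50 and 15/50, as tabulated above.

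If the sponsor prefers to keep a verdict, it would need a stated confidence bound. For illustration, requiring the two-sided exact 95% upper limit to fall below 30% allows at most 8/50 (upper limit 29.1%; chance of passing at a true 30% is 1.8%). That would be a formal test, and 5.1 would have to change.

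The recommended change costs only text in three places. Sample size, data collection and safety oversight stay as they are. The downside is that a result of 15/50 or fewer no longer carries an automatic label; the study reports an estimate and an interval in its place.
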